10 STUDY AND TREATMENT DURATION

10.1 Duration per patient

The overall study duration for each patient is 90 days after baseline.

10.2 Study period

Overall study duration: 9 Months, including 6 Months inclusion period and 90 days of patient participation after last inclusion.

11 STATISTICS

11.1 Planned Analysis

The description of all parameters recorded will be presented by group and for overall population.

Quantitative parameters will be described using the following summary descriptive statistics: number of non-missing values, mean, standard deviation, median, first and third quartiles, and minimum and maximum values.

Qualitative parameters will be described overall using frequencies and percentages. Percentages will be calculated on the number of non-missing observations.

The test and control groups will be compared on the primary and secondary outcomes of the study.

It will be proven that the test group is superior to the control group.

First, normality tests (e.g. Kolmogorov-Smirnov or Shapiro-Wilk test) will be used to assess the normality of the distribution. According to data distribution, t-test or Mann-Withney u-test will be applied for continuous variables, such as the gingiva abraded and gingival relief scoring.

For categorical variables, Pearson's Chi square test or Fisher's exact test will be used.

Within a certain group, tests will be used to explore the time effect, i.e. evolution between baseline and post-baseline measurements. Wilcoxon's test or Student's test for pairwise comparisons will be used, depending on the normality of the distribution.

Any imbalance between-treatment groups in baseline measurements, despite randomization, will be researched and this analysis will be performed using Student's test or Wilcoxon's test for quantitative parameters and Chi-square test or a Fisher's exact test for qualitative parameters.

In case of any imbalance observed, an ANCOVA including the treatment group with the baseline as covariate(s) for quantitative parameters or a logistic regression with the same parameters will be done instead.

In order to provide unbiased and informative findings, no replacement of missing values is planned for any parameters. In all applicable cases, reported analysis will mention the number of missing values for each outcome relatively to the considered analysis set.

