11.2 Level of significance

The level of significance for all comparisons is set at 0.05 using two-tailed tests.

Confidence level is set at 0.95 (two-sided) for all primary and secondary endpoints.

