11.8 Sample Size

The sample size calculation is based on a preliminary study evaluating the primary criteria (macro-relief scoring changes between D0 and D90 after manual compared to electric brushings). In this preliminary study, we have measured a threshold value of $\Delta E = 0.67$ on the primary criteria between manual brushing and electric brushing, associated with a standard deviation of 0.84. Using a

bilateral two-group test with a 0.05 two-sided significance level and a power (1- β) of 0.80 yielded a sample size of 25 subjects per group (34 subjects when considering a power (1- β) of 0.90).

We can add 20% for potential dropouts. Thus, 30 subjects per group is evaluated, i.e. 60 subjects are required in total.

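### Baseline gingival abrasion is adjusted for only if a baseline test shows imbalance, so the primary method depends on the data and power is given up

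*Protocol*

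**What the plan says.** Protocol section 11.1 sets out a sequence of data-dependent steps.

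1. Normality is tested first, and the result decides the between-group test: "According to data distribution, t-test or Mann-Withney u-test will be applied for continuous variables". The gingival relief score, which is the primary endpoint, is named as an example of such a variable.
2. The arms are then compared at baseline: "Any imbalance between-treatment groups in baseline measurements, despite randomization, will be researched", using Student's or Wilcoxon's test for quantitative parameters.
3. Adjustment depends on that comparison: "In case of any imbalance observed, an ANCOVA including the treatment group with the baseline as covariate(s) for quantitative parameters" is carried out in place of the default test.

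Section 11.2 adds: "The level of significance for all comparisons is set at 0.05 using two-tailed tests". No other threshold for imbalance is given. Section 11.5, on the primary endpoint, describes how the photographs are scored but names no model that would override section 11.1. Section 11.8 bases the sample size on "macro-relief scoring changes between D0 and D90 after manual compared to electric brushings", so a baseline GA score is expected for every patient. The schedule in section 9.1 confirms that GA is assessed at both visits.

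**The concern.** There are three problems with the rule.

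- **Wrong trigger.** With sound randomisation, any baseline difference is due to chance. A significance test on it does not show how strongly the covariate predicts outcome, and that prediction is what makes adjustment worthwhile. Baseline GA is the natural predictor of day-90 GA. Under this rule it would usually be left out.
- **Primary method unknown in advance.** The primary p-value may come from a t-test, a Mann-Whitney test or an ANCOVA, and which one is settled only after the data are examined. These are not interchangeable. Section 11.8 sizes the trial on a mean difference, which is not what Mann-Whitney tests.
- **Open trigger.** The rule refers to any imbalance and to one or more covariates. It does not list the variables that count, give a threshold specific to this decision, or say which covariates then enter. Two analysts could apply it differently to the same data.

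What is at stake is precision on the primary endpoint of a 60-patient trial planned at 80% power, and a clear statement of which analysis is primary.

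**Working it through.** **Inputs.** Two-sided alpha is 0.05 (section 11.2). The difference is 0.67 and the SD 0.84, with 25 per group at 80% power and 34 at 90% (section 11.8). The correlation ρ between baseline and day-90 GA is not in the protocol, so 0.3, 0.5 and 0.7 are assumed.

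**The plan's own figure.** n per group = 2(z₀.₉₇₅ + z_power)² SD²/Δ².

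- 80%: 2 × (1.960 + 0.842)² × 0.84²/0.67² = 24.7, so 25.
- 90%: 2 × (1.960 + 1.282)² × 0.84²/0.67² = 33.0, which rounds up to 34.

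Both stated figures reproduce. The t-distribution gives 78.9% power at 25 per group for the unadjusted test.

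**What adjustment gains.** Assume equal variance σ² at both visits.

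- Variance of change = 2σ²(1 − ρ). ANCOVA residual variance = σ²(1 − ρ²). The ratio is (1 + ρ)/2.
- Relative to an unadjusted day-90 score, the ratio is 1 − ρ².

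Section 11.8 describes change, so reading A takes 0.84 as the SD of change, with change as the analysed variable. Section 11.1 does not name the analysed variable, so reading B takes 0.84 as the SD of the day-90 score and analyses that score.

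| ρ | Reading | Variance ratio | n per group for 80% power with ANCOVA |
|---|---|---|---|
| 0.3 | A | 0.65 | 17 |
| 0.5 | A | 0.75 | 19 |
| 0.7 | A | 0.85 | 21 |
| 0.3 | B | 0.91 | 23 |
| 0.5 | B | 0.75 | 19 |
| 0.7 | B | 0.51 | 13 |

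**The plan's rule against ANCOVA in every case.** 100,000 simulated trials per setting, normal data, 25 per group. The rule was applied as a baseline GA t-test at 0.05, then ANCOVA if significant and the unadjusted t-test otherwise. The normality step was not simulated.

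| ρ | Reading | Power, plan's rule | Power, always ANCOVA | Gain (points) |
|---|---|---|---|---|
| 0.3 | A | 80.2% | 92.3% | 12 |
| 0.5 | A | 80.0% | 88.6% | 9 |
| 0.7 | A | 79.2% | 84.2% | 5 |
| 0.3 | B | 79.1% | 81.8% | 3 |
| 0.5 | B | 79.8% | 88.4% | 9 |
| 0.7 | B | 80.9% | 96.9% | 16 |

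ANCOVA was triggered in about 5% of simulated trials, so the rule recovers at most about 2 points over the unadjusted test. At ρ = 0.5 under the planned effect, the adjusted and unadjusted tests disagreed on significance in about 13% of trials.

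**Type I error.** It was 3.7% to 4.7% for the plan's rule and about 5% for ANCOVA in every case.

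**How often chance triggers adjustment.** Section 9.1 lists six baseline assessments: plaque, bleeding, recession, pocket depth, abrasion and colour. If all six counted and were independent, at least one would reach p < 0.05 in 1 − 0.95⁶ = 0.265 of trials, about 26%. If only baseline GA counts, the figure is 5%.

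**The case against.** The strongest reply is that a change score already uses the baseline. The better baseline predicts day 90, the less ANCOVA adds to an analysis of change. At 24 per group under reading A, the plan's rule against ANCOVA gave 0.765 and 0.798 at ρ = 0.8, and 0.780 and 0.789 at ρ = 0.9. With ρ unknown, the gain could be as little as about 1 point. This stands as a limit on the size. It does not defend the rule, because ANCOVA did better at every correlation examined and held its nominal error rate.

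Four further points qualify the finding.

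- The departure from nominal type I error is towards conservatism. The baseline trigger brings no false-positive risk in these simulations.
- The rule is written in advance, and section 6.5 says statistical procedures are blind to treatment. This is a poor conditional algorithm, not free choice after the event, although the undefined trigger leaves some latitude.
- The six baseline measures are probably correlated, because erythema, inflammation, bleeding and recession are themselves components of the GA score. The 26% is therefore approximate and probably too high. The covariate may also be meant as each parameter's own baseline, which returns the figure to 5%.
- GA is a 0 to 15 sum of ordinal items in patients without periodontal disease, so skew and floor effects are plausible. The gains were computed for normal data and not shown for such a distribution.

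**Conclusion.** The concern holds. The protocol itself fixes a rule in which the primary method depends on a normality test and a baseline significance test, and that rule gives up precision the trial could have from data it already collects. At the protocol's own difference, SD and 25 per group, the loss is about 9 points of power at ρ = 0.5 under either reading of the SD, and about 3 to 16 points for ρ from 0.3 to 0.7. It shrinks to about 1 point if change is analysed and ρ is near 0.9, and it is small if the day-90 score is analysed and ρ is about 0.3 or less. These sizes rest on an assumed correlation, normal data and baseline GA as the only trigger. That adjustment should be prespecified does not depend on the exact size. The planned test is not invalid; it is inefficient and leaves the primary analysis open. The change should be made.

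**What to change.** In sections 11.1 and 11.5, state one primary analysis: ANCOVA of day-90 GA on treatment and baseline GA, used whatever the baseline comparison shows, reported as an adjusted mean difference with its 95% confidence interval. Using change as the outcome, with the same baseline covariate, gives the same treatment estimate.

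- Remove the baseline significance tests as a trigger and describe baseline by arm instead.
- Remove the normality test as the selector. Name a Mann-Whitney test or a rank-based ANCOVA as a sensitivity analysis, which also covers possible skew in the score.
- Apply the same baseline-adjusted approach to the quantitative secondary endpoints (plaque index, bleeding, recession). For bleeding, first settle whether the analysed variable is dichotomous or a percentage of sites, since section 5.2.2.4 describes both.

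The cost is rewording two sections and one degree of freedom. No additional patients, visits or measurements are needed, because baseline GA is already collected.

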11.2 Level of significance

The level of significance for all comparisons is set at 0.05 using two-tailed tests.

Confidence level is set at 0.95 (two-sided) for all primary and secondary endpoints.

11.3 Patient selection for analyses

There will be three analysis populations defined for the study:

- The Safety population (SAF) will include all patients who signed an informed consent form.
Safety analyses will be performed on the SAF population.
- The Full Analysis Set (FAS) population will include all patients who signed an informed consent form and performed the study procedures, whatever their assigned treatment group by randomization.

Description of demographic and baseline characteristics as well as analyses of primary and secondary endpoints (other than safety endpoints) will be performed on the FAS population.

- The per protocol (PP) population will include patients from the FAS population without major protocol deviation that might significantly affect the completeness, accuracy, and/or reliability of the study data. Deviations involving possible bias regarding the primary endpoint analysis will be considered as major deviations. Protocol deviations will be further defined in the statistical analysis plan.

The PP population will be used for the supportive analyses of the primary and main secondary endpoints (other than safety endpoints).

11.4 Description of baseline characteristics

Appropriate descriptive methods (means, standard deviations, minimum, median, maximum, lower and upper quartiles, number of observations, percentages and 95% confidence intervals) will be used to describe demographics data and other baseline characteristics.

These analyses will be performed on the SAF population. Some parameters could also be described on FAS and/or PP populations if more than 10% are excluded from SAF population.

11.5 Analysis of the primary endpoint

All parameters listed in Section 5.2.2 will be documented and compared between treatment groups.

Macro-relief scoring: The technique consists of acquiring macroscopic photographs of each gingival quadrant at each time point. Observers will score those photographs in a double-blind manner by comparing the different photographs with a photonumerical reference scale used as standard. This scale will first be retained by observers as being representative of the different grades of gingival abrasion: from 0 (no abrasion) to 15 (severe gingival abrasion) according to the following table:

Score Criteria	0	1	2	3
Erythema	None	Small (surface 0 to $\frac{1}{4}$)	Medium (surface $\frac{1}{4}$ to $\frac{1}{2}$)	Large (surface $> \frac{1}{2}$)
Inflammation	None	Small (surface 0 to $\frac{1}{4}$)	Medium (surface $\frac{1}{4}$ to $\frac{1}{2}$)	Large (surface $> \frac{1}{2}$)
Bleeding	None	Slight	Moderate	Severe/expanded
Recession	None	Small (≤ 2 mm)	Medium (3 to 5 mm)	Large (> 5 mm)
Erosion	None	Slight	Moderate	Severe/expanded

11.6 Analysis of the secondary endpoints

All parameters listed in Section 5.1.2 will be documented and compared between treatment groups.

Gingival coloring intensity: The technique consists of acquiring macroscopic photographs of each gingival quadrant, including an internal colored reference chart in the vicinity of the photographed gingival tissue, at each time point. Next, using an image analysis software, each photograph will be calorimetrically reconverted to be recalibrated following the colored reference chart. Then, the coloring intensity in each zone of interest [marginal (cervical free gingiva, CFG), interdental (papillary free gingiva, PFG) and mid- gingival (attached gingiva, AG)] around each tooth in each quadrant, will be extracted by observers in a double-blind manner using the color picker tool.

All parameters listed in Section 5.2.2 will be documented and compared between treatment groups.

11.7 Analyses of safety endpoints

Safety will be assessed with the collection of adverse events throughout the study. The number and percentage of patients with at least one AE will be calculated with its 95% confidence interval (CI). All the AEs will also be described by system organ classes (SOC) and preferred terms (PT) and will be classified as serious or not, related to the device or not. All the serious AEs related to the device will be described. A listing describing the following data will be provided: classification as SAE, intensity, imputability to procedure, imputability to Investigational Product, action taken, corrective treatment, outcome, delay of occurrence and duration.

The safety analyses will be performed on the SAF population.

11.8 Sample Size

The sample size calculation is based on a preliminary study evaluating the primary criteria (macro-relief scoring changes between D0 and D90 after manual compared to electric brushings). In this preliminary study, we have measured a threshold value of $\Delta E = 0.67$ on the primary criteria between manual brushing and electric brushing, associated with a standard deviation of 0.84. Using a

bilateral two-group test with a 0.05 two-sided significance level and a power (1- β) of 0.80 yielded a sample size of 25 subjects per group (34 subjects when considering a power (1- β) of 0.90).

We can add 20% for potential dropouts. Thus, 30 subjects per group is evaluated, i.e. 60 subjects are required in total.

11.9 Criteria for the termination of the study

See section 7.3.

12 SOURCE DATA AND SOURCE DOCUMENTS

12.1 Definitions

12.1.1 *Source Documents*

Source documents are defined as original documents, data and records (e.g. hospital records, clinical and office charts, laboratory notes, memoranda, patient diaries or evaluation check lists, pharmacy dispensing records, recorded data from automated instruments, copies or manuscripts certified after verification as being accurate copies, microfiches, photographic negatives, microfilm or magnetic media, x-rays, patient files, records kept at pharmacy, at the laboratories and at medico technical departments involved in clinical study).

12.1.2 *Source Data*

Source data are defined as all information in original records and certified copies of original records of clinical findings, observations or other activities in a clinical study necessary for the reconstruction and evaluation of the study. Source data are contained in source documents (original records or certified copies).

12.1.3 *Direct Access*

Direct access is defined as the permission to examine, analyze, verify and reproduce any records and reports that are relevant to evaluation of a clinical study.

12.2 Permission of Access

The Investigator will permit study-related monitoring, audits, IRB/IEC review and regulatory inspections, by providing direct access to primary patient data (i.e. source data) which support the data on the study's eCRFs, e.g. general practice charts, hospital notes, appointment books, original laboratory records.

Because this enters within the realm of patient confidentiality, this fact must be included in the Informed Consent Form to be signed by the patient in line with the General Data Protection Regulation (EU) 2016/679 (GDPR).

Any party, e.g. local and foreign regulatory authorities, the Sponsor and/or authorized representatives of the Sponsor such as monitors and auditors, with direct access should take all reasonable precautions within the constraints of the applicable regulatory requirements to maintain the confidentiality of patient identities and Sponsor proprietary information.

13 ASSESSING AND REPORTING OF ADVERSE EVENTS

13.1 Definitions

According to the article R. 1123-39 1°; 2°; 6°; and 8° of the French public health code, the following definitions apply:

13.1.1 *Adverse Event (AE)*

An adverse event is any untoward medical occurrence, unintended disease or injury, or untoward clinical signs (including abnormal laboratory findings) in subjects, user or other persons, whether or not related to the Investigational Product. This definition includes events related to the Investigational Product or the comparator and events related to the procedures involved.

13.1.2 *Adverse Reaction (AR)*

An adverse reaction is defined as an adverse event related or likely to be related to the investigational product".

13.1.3 *Serious Adverse Event/Reaction (SAE/SAR)*

An adverse event/reaction that

- results in death,
- is life-threatening,

NOTE: The term "life-threatening" in the definition of "serious" refers to an event in which the patient was at risk of death at the time of the event; it does not refer to an event which hypothetically might have caused death if it were more severe.

- requires inpatient hospitalization or prolongation of existing hospitalization,
- results in persistent or significant disability/incapacity, or
- is a congenital anomaly/birth defect,
- is an important medical event.

*Planned hospitalization for a pre-existing condition, or a procedure required by the clinical study protocol, without serious deterioration in health, is not considered a SAE.

Medical and scientific judgment should be exercised in deciding whether expedited reporting is appropriate in other situations, such as important medical/medically significant events that may not be immediately life-threatening or result in death or hospitalization but may jeopardize the patient or may require intervention to prevent one of the other outcomes listed in the definition above. These should usually also be considered serious.

13.1.4 *Unexpected Serious Adverse Reaction (USAR)*

An unexpected adverse reaction is any adverse reaction whose nature, severity or outcome does not match with the information relating to the products, acts performed, and methods used during the research.

For each adverse reaction, the sponsor must assess whether or not it is unexpected.

The assessment of the unexpected nature of an adverse reaction is made on the basis of the information described in the protocol or instructions for use, relating in particular, if applicable, to the acts and methods practiced or in products being researched or used for research purposes.

If the adverse reaction relates to a health product used for the purposes of the trial, it is appropriate in order to determine the unexpectedness of this effect, to refer to the information contained in the relevant standards if the product is used in accordance with these standards [for example the summary of product characteristics of marketing authorization (Marketing Authorization) for a drug, when that drug is used, as part of the test, in accordance with this MA].

13.1.5 New security event

Any new data or information that could result in:

- A re-evaluation of the benefit risk ratio of the risks of the research or the Investigational Product
- Modifications of the use of the Investigational Product, the study conduct or the study documents
- A temporary or permanent halt of the research
- A modification of the research protocol or any similar research protocol

13.2 Organization and evaluation

The study period during which (serious) adverse events will be recorded/reported is defined as the period from patient inclusion to the end of study participation.

The clinical course of each (serious) adverse event will be followed up until the event (or its sequelae) resolves or stabilizes at a level acceptable to both the Investigator and Sponsor,

Every effort will be made by the Investigator to explain each AE and assess its causal relationship to the Investigational Product. The Investigator will use the following definitions and categories to assess adverse events:

Seriousness:

- No: no fulfilment of Serious AE criterion
- Yes: fulfilment of SAE criterion (see section 13)

Severity/Intensity:

- Mild: Transient or mild discomfort, no modification of procedure or medical intervention required
- Moderate: Discomfort causes interference with usual activities, no or minimal modification of procedure or medical intervention required
- Severe: Inability to work or to do usual activity, medical intervention indispensable

There is a distinction between the terms “severe” and “serious” for an AE. Severe is a measurement of intensity; thus, a severe reaction is not necessarily a SAE. For example, a headache may be severe in intensity, but would not be serious unless it met one of the criteria for SAEs listed in section 13.1.3.

Action undertaken in regard to the Investigational Product:

- None
- Investigational Product postponed
- Investigational Product discontinued

AE therapy:

- Yes: remedial treatment necessary
- No: remedial treatment unnecessary

Final outcome:

- Recovered without sequelae
- Recovered with sequelae
- Ongoing
- Unknown
- Death
- Improving/worsening

Causality (relationship with the Investigational Product):

- Certain: temporal correlation plausible, other causes excluded
- Probable: temporal correlation reasonable, other causes unlikely
- Possible: temporal correlation reasonable, other causes possible, not assessable
- Unlikely: No temporal correlation, other causes probable, not assessable
- Not related: definitely no causal relationship (see section 10.1.8)

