7.3.1 Discontinuation Criteria Related to the Study

Criteria for discontinuation / termination of the entire clinical study include (non-exhaustive list):

- Unexpected high frequency of adverse (device) reactions / adverse (device) effects during the study which does not justify a continuation of the study
- Patients cannot be recruited in sufficient numbers

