9.3 Procedures at Each Visit

Study procedures are described in the tabular overview provided in Section 6.2.

A maximum of 2 visits will be scheduled as follows:

- Screening/Baseline visit at Day 1 (D1), with baseline oral assessment in case of inclusion
- Follow-up visit: at 90 days

Screening/Baseline Visit (Day 1):

This initial study phase consists of a pre-screening of the patients. During routine visits, possible patients will be selected. The patients will be informed on the background of the study and a written explanation will be given concerning the objectives and the study procedures. They all will request to give their written consent prior to enrolment into the study.

The following procedures will apply:

- Explanation to the patient of the purpose of the study and planned oral hygiene procedures;
- Inclusion/Non-Inclusion criteria;
- Patient agreement to comply with study requirements and informed consent form signing;
- Randomization;
- Supply of the Investigational Product (by the operator);
- Plaque measurement (PI);
- Inflammation assessment (BOP);
- Gingival recession assessment (REC);
- Pocket depth probing (PD);
- Dental Photographs and analyze of Gingival macro relief coloring (GA);
- Tooth brushing session;
- Oral Hygiene Instructions.

Subsequent visit date will be scheduled at the end of this visit.

Follow-up visit at 90 Days

The following procedures will apply:

- Plaque measurement (PI)
- Inflammation assessment (BOP);
- Gingival recession assessment (REC);
- Pocket depth probing (PD);
- Dental Photographs and analyze of Gingival macro relief coloring (GA);
- Dental photograph;
- Toothbrush collection (by the operator);
- Assessment of toothbrush usage (patient reported);
- Assessment of toothbrush usage (brush head wear assessment);

- Assessment of toothpaste usage (paste weighed)
- Adverse events collection.

9.4 Assessment of Compliance.

Upon completion of clinical assessments, all manual toothbrushes as well as all brush heads will be collected by the operator, and the age of the brush or brush head will be assessed by asking the participants the number of weeks the brush or brush head was used. After completion of the study, the operator will assess all manual toothbrushes as well as all brush heads for brush wear according to the method described by Conforti *et al.* on a 0–4 scale (Conforti *et al.*, 2003).

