13.3 Role of the Investigators

All AEs occurring during the study period set out in this protocol, observed by the Investigator or reported by the participant, will be recorded in the eCRF (adverse event form) according to the general instructions for completion.

If the AE is Serious (see Section 13.1.3), the investigator must complete the "Serious Adverse Event" form at the time the SAE is detected, in addition to the "Adverse Event" form in the e-CRF.

The investigator will notify the sponsor, as soon he/she becomes aware of all SAEs (whether or not attributed to the product under investigation), new safety issues, without waiting for results of clinical outcome or of additional investigations, unless if the protocol specifies that the event does not need immediate notification.

The initial SAE report will be as complete as possible, including date of onset and end date, severity, seriousness, assessment of relatedness to IP, other suspect drug or device, study procedures and action taken.

The initial notification of a serious adverse event to the sponsor is the subject of a written report and must be followed quickly by one or more detailed written report(s) in order to follow the evolution of the case or add information.

Any information not available at the time of the initial SAE report will be documented on a follow-up report and SAE will be followed up until resolution or the event is considered stable. The SAE forms must be printed and supplied immediately (within max. 24 hours after SAE awareness) to the vigilance department of Philips:

Philips consumer Support
[name]
[contact]
[contact]

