19.2 Appendix 2: Philips Sonicare ProtectiveClean® Instructions for use

Philips Sonicare ProtectiveClean® - ©2014 Koninklijke Philips Electronics NV (KPENV).

The Sonicare toothbrush complies with the safety standards for electromagnetic devices. If you have a pacemaker or other implanted device, contact your physician or the device manufacturer of the implanted device before you use the Sonicare.

Package Insert

General Description

IMPORTANT

Read this user manual carefully before you use the appliance and save it for future reference.

DANGER

-Keep the charging base away from water.

Do not place or store it over or near water contained in a bathtub, washbasin, sink etc. Do not immerse the charger in water or any other liquid. After cleaning, make sure the charger is completely dry before you connect it to the mains.

WARNING

-The mains cord cannot be replaced. If the mains cord is damaged, discard the charger.

- Always have the charger replaced with one of the original type in order to avoid a hazard.
- Do not use the charger outdoors or near heated surface.
- Check if the voltage indicated on the appliance corresponds to the local mains voltage before you connect the appliance.
- If the appliance is damaged in any way (brush head, toothbrush handle or charger), stop using it. This appliance contains no serviceable parts. If the appliance is damaged, contact the Consumer Care Centre in your country (see chapter 'Warranty and support').
- This appliance can be used by children and by persons with reduced physical, sensory or mental capabilities or lack of experience and knowledge if they have been given supervision or instruction concerning use of the appliance in a safe way and understand the hazards involved. Cleaning and user maintenance shall not be made by children without supervision.
- Children shall not play with the appliance.

CAUTION

- Do not clean the brush head, handle or the charger in the dishwasher.
- If you have had oral or gum surgery in the previous 2 months, consult your dentist before you use the toothbrush.
- Consult your dentist if excessive bleeding occurs after using this toothbrush or if bleeding continues to occur after 1 week of use. Also consult your dentist if you experience discomfort or pain when you use the Philips Sonicare.

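### Adverse events are to be recorded from inclusion (13.2, 11.7), but the flow charts and Section 9.3 schedule their collection only at Day 90, leaving Day 1 and early leavers to spontaneous reporting

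*Protocol*

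**What the plan says.** Section 13.2 states that the period for recording and reporting adverse events is "defined as the period from patient inclusion to the end of study participation". Section 11.7 agrees: "Safety will be assessed with the collection of adverse events throughout the study".

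The schedules are narrower. Section 9.3 opens with "A maximum of 2 visits will be scheduled as follows", meaning Day 1 and Day 90. The Day 1 list includes probing and "Tooth brushing session" but no adverse event step. "Adverse events collection" appears only in the 90-day list. The flow charts in the synopsis and in Section 9.1 each have an adverse event row with one mark, in the Day 90 column.

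Other provisions bear on this:
- Section 13.3: events in the study period "observed by the Investigator or reported by the participant, will be recorded in the eCRF (adverse event form". Serious events go to the sponsor within 24 hours of awareness.
- Section 7.3.3: the withdrawal page takes the date, the initiator and the reason. An adverse event is one of the listed reasons.
- Section 11.3: the safety population is everyone who signed consent.
- Section 7.3.1: the study may be stopped for "Unexpected high frequency of adverse (device) reactions / adverse (device) effects during the study". No threshold or review time is given.

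**The concern.** The safety section and the schedule of assessments do not describe the same collection. Site staff work from the visit list and the flow chart, and these tell them to ask about adverse events once, about three months after the exposure begins.

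Two groups of events lose a systematic enquiry. The first is non-serious events on Day 1, the only visit at which use of the brush is directly supervised. The second is events in patients who do not return at Day 90, where the event is not the reason given for leaving. These patients stay in the denominator of the percentage that Section 11.7 reports with a confidence interval. If nobody asks them, they count as event-free. The schedule also means that no solicited adverse event data reach the Section 7.3.1 criterion until the first Day 90 visits.

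**Working it through.** **1. Texts side by side.**
- Window: inclusion to end of participation (13.2); throughout the study (11.7).
- Scheduled collection: Day 90 only (synopsis flow chart, 9.1 flow chart, 9.3).
- Inclusion falls on Day 1, so events after the Day 1 probing and brushing lie inside the window but have no scheduled enquiry. No early-termination visit is described.

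**2. The plan's dropout allowance (11.8).** The sample size reproduces. With a difference of 0.67, SD 0.84, two-sided alpha 0.05 and 80% power, n = 2 × (1.96 + 0.842)² × (0.84/0.67)² = 24.7, so 25 per group. At 90% power the formula gives 33.03, so 34. Both match the protocol. Adding 20% gives 25 × 1.2 = 30 per group, 60 in total. The allowance is therefore 60 − 2 × 25 = 10 patients, and 10/60 = 16.7%. This point changes none of these figures.

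**3. Effect on the percentage in 11.7.** Take the safety population as the 60 planned patients (it is defined by consent, so it could be somewhat larger). Suppose all 10 allowed losses occur before Day 90.
- If none of the 10 has an unrecorded event, nothing is lost.
- If events are as frequent in leavers as in completers and none of the leavers' events is recorded, the reported percentage is 50/60 = 0.83 of the true one.
- If every leaver had an unrecorded event, the shortfall is 10/60 = 16.7 percentage points. This is an outer limit, because withdrawals due to an adverse event are recorded under 7.3.3.

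**4. Timing of the first scheduled collection.** Inclusion lasts 6 months (10.2). Assuming even accrual, 60/6 = 10 patients per month, and the first Day 90 visit comes at about month 3. About 10 × 3 = 30 of 60 are then already included. If 30% to 70% of inclusions fall in the first half, the range is 60 × 0.3 = 18 to 60 × 0.7 = 42. With even accrual, about 30 of 60 have reached Day 90 when inclusion closes.

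**The case against.** The strongest reply is that a recording window and a visit at which events are asked about are different things. A Day 90 enquiry can cover the whole interval for completers, and several provisions work before then. Section 13.3 obliges the investigator to record any event seen or reported from inclusion onward, including on Day 1. Serious events are notified within 24 hours of awareness. Section 13.4 gives the sponsor continuous safety evaluation. Under Section 14.1.2 the monitor opens the eCRF at each inclusion and each theoretical follow-up visit, and the routine checks cover serious and non-serious events. Photographs taken just after the first brushing are scored for bleeding and erosion, so visible local effects are documented on Day 1. Section 4.3 expects very few adverse effects.

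All of this stands, and it rules out several stronger readings that a reader might infer:
- *That early events cannot be recorded at all.* Section 13.3 provides the route; what is missing is a scheduled enquiry.
- *That 7.3.1 has no data for three months.* It has unsolicited reports, serious event notification and the monitor's checks.
- *That events causing drop-out are the likeliest to be missed.* Section 7.3.3 lists an adverse event as a withdrawal reason, so these are among the better captured.
- *That participants are never told to report between visits.* The consent pages are not in the text at hand and may say so. The appended manual's advice, "Consult your dentist if excessive bleeding occurs after using this toothbrush or if bleeding continues to occur after 1 week of use", sets no trial contact and contradicts nothing.
- *That the shortfall differs by arm.* The schedule is the same in both. Participants know which brush they use, so unequal reporting is conceivable, but the protocol gives no basis for its size.

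What the reply does not remove is the mismatch. Section 13.3 captures what is noticed or volunteered, the monitor reviews entries and does not question patients, and the photographs are endpoint data that do not cover pain or events during home use.

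**Conclusion.** The point holds as an inconsistency between the safety sections and the schedules. Adverse events are solicited only at Day 90. Non-serious Day 1 events, and events in early leavers other than the stated reason for leaving, depend on spontaneous reporting. Day 1 events in completers may still be recovered at Day 90 by recall; for early leavers there is no later enquiry.

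The reported percentage may be too low, by an amount that the protocol cannot fix. Up to about 10 of 60 patients (16.7%) could leave without being asked. That figure assumes the whole dropout allowance is used before Day 90, and it counts unasked patients, not missed events. The 30 of 60 included before the first scheduled collection rests on assumed even accrual (18 to 42 under the range shown). The primary endpoint, its analysis and the sample size are unaffected. This is a modest flaw that is worth correcting because it is cheap to correct.

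**What to change.** Reconcile the schedules with Sections 13.2 and 11.7:
- In Section 9.3 and in both flow charts, mark adverse event collection on Day 1, after the supervised brushing, as well as on Day 90.
- Add an adverse event enquiry to the withdrawal page in Section 7.3.3, so that a patient leaving early is asked about any event and not only about the reason for leaving.

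This takes a few words in Section 9.3, one mark in each flow chart, an eCRF prompt on Day 1 and an item on the withdrawal page. It needs no extra visit or staff. The small downside is that more minor events will be recorded. Patients lost without any contact will still not be asked, so the safety report should state how many there were in each group.
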